# 7.5 HIPAA – Protection of Patient Information

All data collected in the process of pre-screening, screening, and conducting the proposed research will be stored and maintained locally and centrally in compliance with HIPAA regulations. Access to study data will be secure with limited, password-protected access. Only study personnel who are IRB approved will have access to data collected as part of these studies. Data collected locally for the BetaFat study will be stored on a server that is maintained with the highest stringency of protection. Similarly, data transferred to the RISE CoC will be stored on a server that is maintained with the highest stringency of protection.

# 8 ADVERSE EVENT REPORTING

An adverse event is defined as any medical problem experienced by a BetaFat participant whether or not considered intervention-related by the clinical center staff. The timely and complete reporting of adverse events is a critical requirement in the conduct of this trial. This trial will be conducted under an IDE for participants without diabetes and will comply with all FDA reporting requirements.

# 8.1 Definition of Serious Adverse Events

- a. The event results in an inpatient hospitalization (any overnight stay associated with an admission).
- b. The event results in the prolongation of a hospital stay.
- c. The event results in permanent or severe disability.
- d. The event results in death.
- e. A pregnancy results in a congenital anomaly.
- f. The event results from an overdose (either accidental or experimental) of the study medication.
- g. The event is life-threatening.
- h. Treatment is required to prevent a serious event, as defined above.

# 8.2 Non-serious Adverse Events

Non-serious are all AEs which do not meet the above criteria for "serious".

# 8.3 Reporting Adverse Events

AEs will be ascertained in an unbiased manner using standard questions that are identical and administered identically to participants in both treatment arms. To accomplish this, AEs will be reported on a standard form that is completed by the study staff at each regular study visit. Targeted non-serious AEs (e.g., abdominal pain) are ascertained by asking questions relating to

specific events of import in prediabetic or diabetic participants as well as side effects that may be associated with any of the study treatment arms. AEs also include any significantly abnormal physical finding identified on examination and any significantly abnormal laboratory result obtained on the patient between visits or at the time of the visit.

In order to facilitate timely reporting of SAEs, the clinical center staff who learn of an SAE must enter the completed RISE Consortium Serious Adverse Event Report prior to the close of the following business day.

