## 3.4.2 Gastric Band Arm

The LapBand will be placed and participants will be followed according to standard clinical practice under the supervision of [name]. Costs for these procedures will be paid by Allergan in the form of an unrestricted research grant. Pre-operative evaluation will include a psychological evaluation, a cardiac evaluation with EKG and stress testing, evaluation by an anesthesiologist, a chest X-ray and clinical lab testing (CBC, chemistries, UA, PT/PTT, hepatitis panel and, for women, pregnancy test). Participants also meet with the bariatric nutritionist for education on dietary restrictions that will apply once the band is in place.

Surgeries for placement of LapBands will be performed by [name] at the Keck Hospital of USC. The procedure is done laparoscopically on outpatients. Patients see [name] 2 weeks after surgery for wound check and suture removal. Band adjustments are performed by [name], members of his bariatric surgical team, and/or [name]. Adjustments will commence ~4 weeks after surgery and will recur every 1-3 months at the time of regular research visits. Adjustments will be made based on specific criteria consisting of symptoms of satiety and hunger, dietary history, and weight loss. Patients will revert to liquid diet for 24-48 hours after band adjustments and advance diet over the next 3-5 days. The bariatric team has an on-call system to evaluate and treat patients who have symptoms related to their bands. Post-operative laboratory assessments include CBC; chemistries; vitamin B1, B6 and B12 levels; ferritin; and 25(OH) vitamin D (see Table 2 for testing schedule).

Although both groups will be on active treatment, it is possible that glycemic control could deteriorate to a point of needing additional therapies. We will be monitoring HbA1C at six month intervals. If a value is >8.0%, we will repeat it in one month and, if it remains >8.0% we

will consider the subject to have reached a safety endpoint for the trial. We will perform end-of study visits (scheduled for 24 months in Table 3) and refer the subject for care of his/her diabetes.

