# 6.3 Visit Windows

Follow-up visits are scheduled every two months after randomization during the first year and every three months during the second year. Each participant will have a visit calendar generated at the time of randomization and they will be encouraged to complete visits within 1 week before or after the scheduled date. However, it is likely that some visits will not be completed within this window. To maximize the amount of on-trial information available from each participant, we will define visit windows as (a) first year after randomization: from two weeks before to six weeks after a scheduled visit; and (b) second year after randomization: from one month before to two months after a scheduled visit. Visits that do not occur within these windows will be deemed missed.

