## 7.4 Risk Management

#### 7.4.1 Metformin

To minimize the risk of gastrointestinal side effects, metformin is given with meals, started at a dose of 500 mg/d, and titrated to the target does of 1000 mg bid over a four-week period. If GI side effects develop and are mild, the patient is encouraged to remain on the study medication. If GI side effects are moderate or difficult to tolerate, metformin is reduced to the next lowest dose (for example, 1000 mg bid to 1000 mg + 500 mg; 1000 mg + 500 mg to 500 mg bid; etc.). If symptoms persist, metformin is reduced to the next step. If GI symptoms resolve, metformin is re-escalated by 500 mg per day each week until reaching the previously tolerated dose. The participant will continue on the maximum tolerated dose.

Renal insufficiency increases the risk of lactic acidosis associated with metformin. To asses renal insufficiency, serum creatinine and estimated GFR (eGFR) will be calculated using the CKD-Epi equation (ref . Ann Intern Med. 2009;150(9):604-612.) at screening and every six months on therapy. Participants must have an eGFR of 45 mL/minute/1.73 m^2 or higher to be eligible for the BetaFat study. . Metformin will be discontinued if eGFR is below 30 mL/minute/1.73 m^2. If eGFR  $\geq$ 30 and <45 mL/minute/1.73 m^2 then the RISE Safety Committee will review the case to assess the benefits and risks of continuing treatment, and make a recommendation to the clinical center investigators about whether to continue the participant on metformin.

Metformin will be discontinued temporarily 24 hours before, during, and for 48 hours after any of the following events: 1) procedure involving the injection of contrast dye; 2) surgery or other procedure requiring general anesthesia; 3) any illness that could be associated with hypoxia, circulatory failure, or dehydration; 4) hospitalization. Serum creatinine will be rechecked no sooner than 48 hours after the conclusion of the event and study medication recommenced if appropriate.

To monitor for clinically significant vitamin B12 deficiency, we will follow guidelines in the metformin package insert and perform a complete blood count annually while participants are taking metformin.

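### AE recording is not limited to contacts that both arms share, so the non-serious AE tables are at risk of differential ascertainment favouring metformin

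*Combined protocol and SAP*

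**What the plan says.** Section 8.3 states the aim: "AEs will be ascertained in an unbiased manner using standard questions that are identical and administered identically to participants in both treatment arms". The means is that "AEs will be reported on a standard form that is completed by the study staff at each regular study visit". Section 6.2.8 agrees, with a standardised AE questionnaire at every visit, and Table 6.2 marks an examination at every visit for all participants.

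Two further routes to an AE follow in Section 8.3. One is clinical: "AEs also include any significantly abnormal physical finding identified on examination". The other is "any significantly abnormal laboratory result obtained on the patient between visits or at the time of the visit". The opening of Section 8 is wider still, since any medical problem a participant has counts as an AE. None of this text says whether findings made during bariatric care go on the study AE form.

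The common schedule is in Section 6.3: "Follow-up visits are scheduled every two months after randomization during the first year", then every three months. The contacts that only the band arm has are in Sections 3.4.2 and 4.5: a pre-operative work-up after assignment, a visit "2 weeks after surgery for wound check and suture removal", and band adjustments. On the last, Section 3.4.2 says: "Adjustments will commence ~4 weeks after surgery and will recur every 1-3 months at the time of regular research visits". There is also on-call bariatric cover, and Section 6.2.8 adds six-monthly vitamin and ferritin tests in the band arm only. For metformin, Section 7.4.1 has the dose "titrated to the target does of 1000 mg bid over a four-week period".

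**The concern.** Identical questions at identical visits give comparable data only if nothing else feeds the AE record. Here the definition lets in findings from any examination, and one arm is examined more often, mostly in the first weeks. A short-lived finding has more chances of being seen in the band arm even if the true rates are equal. An abnormality found at the pre-operative evaluation would count although the band is not yet in place.

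The opposite gap affects metformin. Gastrointestinal effects are the main known adverse effects of the drug (Section 7.3.1), and titration is when the dose is rising. Transient events that settle before month 2 depend on spontaneous report or on later recall. Band participants are seen in person over much of the same period. The trial is unmasked (Section 4.6), so nothing offsets this.

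Both effects point the same way, towards a better non-serious AE profile for metformin. Non-serious AEs are tabulated in the format used for the DSMB (Section 8.4), and the DSMB may suggest ending an arm for safety (Section 7.2.2). The trial is also presented as a test of concept for earlier use of banding (Section 1.3), so its harm tables will be read as evidence.

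**Working it through.** The plan gives no figure for AE ascertainment, so there is none to reproduce. The check is a count of scheduled contacts, followed by an illustration.

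**1. Common follow-up visits** (Section 6.3, Table 6.2): months 2, 4, 6, 8, 10, 12, 15, 18, 21 and 24, which is 10 per participant in each arm.

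**2. Band-only scheduled contacts after randomisation** (Sections 3.4.2 and 4.5): pre-operative evaluation, 2-week wound check and first adjustment at about 4 weeks, which is 3.

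**3. Ratio of contacts, band to metformin**
- All three counted: (10 + 3)/10 = 1.3. Unmatched share of band contacts: 3/13 = 23%.
- One not counted (pre-operative evaluation left out, or first adjustment merged with the month-2 visit): (10 + 2)/10 = 1.2. Unmatched share: 2/12 = 17%.
- Neither of those two counted: (10 + 1)/10 = 1.1.
- Findings at band-only contacts never entered as AEs: 10/10 = 1.0 for this route.

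**4. Is the first adjustment separate from month 2?** Two months is about 8.7 weeks. In year 1 the visit window runs from two weeks before to six weeks after the scheduled date, so it opens at 8.7 − 2 = 6.7 weeks and closes at 8.7 + 6 = 14.7 weeks. With surgery at the two-week goal, the first adjustment falls at 2 + 4 = 6 weeks, before the window opens. If surgery comes later than about 6.7 − 4 = 2.7 weeks after randomisation, the adjustment can fall inside the window.

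**5. Metformin gap.** Treatment starts the day after the second baseline visit and titration takes four weeks. The first AE form is due at about week 8.7, which is 4.7 weeks after titration ends. Within the window it may be as late as week 14.7.

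**6. Illustration.** Let p be the chance of an incidental short-lived finding per examination, equal in both arms, and k the number of examinations. Then P(at least one) = 1 − (1 − p)^k. The documents give no p; 0.5% to 5% is assumed.

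| p | k = 10 | k = 13 | Ratio, 13 v 10 | Ratio, 12 v 10 |
|---|---|---|---|---|
| 0.5% | 4.9% | 6.3% | 1.29 | 1.19 |
| 1% | 9.6% | 12.2% | 1.28 | 1.19 |
| 2% | 18.3% | 23.1% | 1.26 | 1.18 |
| 5% | 40.1% | 48.7% | 1.21 | 1.15 |

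With no true difference, recorded findings of this kind would be about 1.2 to 1.3 times as frequent in the band arm, and slightly less at 12 contacts with a high p.

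**The case against.** The strongest reply is that the promise in Section 8.3 is kept on its own terms. It concerns the questions and the form at regular visits, and these are the same in both arms, as is the examination schedule in Table 6.2. The words about examination findings can be read as meaning those examinations only, because the reference to findings between visits is attached to laboratory results. This stands in part: the text is incomplete rather than contradictory. It does not dispose of the point, because Section 8 counts any medical problem as an AE and nothing excludes findings at bariatric contacts.

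Second, the metformin arm is not ignored during titration. Section 3.4.1 says gastrointestinal effects will be monitored, and the stepwise dose changes in Section 7.4.1 imply some contact. This is fair, but no contact is scheduled and no AE form is due before month 2.

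Third, what a wound check finds is often true surgical harm, not a detection artefact. This stands, and it rules out any remedy that takes band-only findings out of the comparison.

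Two stronger readings are tempting. A reader might infer that band adjustments add many further contacts, since monthly adjustments would put 14 of 24 outside the common visits. Section 3.4.2 does not support this: it places recurring adjustments at the regular research visits. A one-month interval does not fit visits held every two to three months, but that is an unresolved wording, not a set of planned extra visits. A reader might also infer that the harm comparison is biased. The documents do not establish that band-only findings enter the AE data, and Section 9 plans no formal between-arm AE analysis. A risk of differential ascertainment is as far as the text goes.

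**Conclusion.** The concern holds as a risk of differential ascertainment in the non-serious AE tables, in the direction that favours metformin. Its documented size is up to 13 scheduled contacts against 10, a detection ratio of about 1.2 to 1.3 for short-lived findings when there is no true difference. Added to this is a metformin titration period with no scheduled AE contact.

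The ratio assumes an equal and constant chance of a finding per examination, findings that do not last from one contact to the next, and entry of band-only findings as AEs. If they are not entered, the ratio for this route is 1.0, and the protocol should say so. It does not apply to lasting events, nor to symptoms that the common questionnaire elicits in both arms. On-call contacts and the band-only laboratory tests are parallel asymmetries that the count leaves out. The laboratory route has the firmer textual basis, because Section 8.3 expressly extends it to results between visits. SAEs depend less on contact frequency, and the primary outcomes are untouched.

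**What to change.** In Section 8.3:

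1. State that findings at bariatric-care contacts and from band-only tests are recorded as AEs. Add a field to the AE form for the contact or test at which each event was first identified: common visit, pre-operative evaluation, band-only contact, band-only laboratory test, or unscheduled/spontaneous.
2. Tabulate non-serious AEs by arm in two tables shown side by side. One covers all sources. The other covers events elicited or found at the common visits and common tests. An event first found at a band-only contact stays in the common-visit table if the common-visit questionnaire also elicits it. No event is dropped, and SAEs from any source stay in the comparison.
3. Give the standard AE questionnaire by telephone to both arms at the same stated times before month 2, counted from start of treatment (first metformin dose or surgery). Counting from randomisation would not align the arms, because surgery follows randomisation by a target of up to two weeks.

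The cost is one form field, one extra table and two short calls per participant by existing staff. Treatment and the primary analysis do not change.

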# 8.4 Tracking Adverse Events

- Serious Adverse Events: SAEs will be monitored by the RISE Safety Monitoring Committee, which will remain blinded to treatment arm. The external DSMB will monitor SAEs by treatment arm. It is important to note that all serious and unexpected AEs must be reported to the CoC, regardless of the drug-related assessment. For example, a patient struck by lightning requires a report, even though this is not likely to be a drug related event.
- Non-serious adverse events: Non-serious AEs are tabulated by the CoC in periodic reports in the same format as is done for the DSMB. Summaries of the AEs are provided to the Safety Monitoring Committee, which reviews this summary during one of its regularly scheduled meetings.
- Safety Monitoring Committee: The Safety Monitoring Committee reviews AEs in a blinded fashion. The committee considers whether changes in the protocol (monitoring, consent process, etc.) are indicated based on the occurrence, frequency, or severity of AEs. The committee also evaluates whether there is any clustering of AEs by clinic. Any concerns on the part of the Safety Monitoring Committee may be referred to the Safety Review Officer and/or DSMB, which can review SAEs in an unblinded manner.
- Safety Review Officer: The Safety Review Officer will review all SAEs in an unblinded fashion and will confirm or reject the causality determination of the SAE to study intervention. As deemed necessary, he/she may contact the local site PI to obtain additional information about the SAE. Any concerns on the part of the Safety Review Officer may be referred to the DSMB.

# 8.5 Emergency Unmasking

Treatments will not be masked in the BetaFat study, so emergency unmasking is not relevant to this study.

# **9 STATISTICAL CONSIDERATIONS**

All analyses will be conducted under the intention-to-treat principle using the treatment as assigned to each subject, and using all available data from all subjects. We will assess the distributional characteristics of all variables and will adjust the analysis accordingly by employing transformations or robust (model free) or nonparametric (distribution free) methods.

## 9.1 Primary Outcomes and Analyses

Two primary outcomes, each measuring ß-cell function, will be used to compare the two intervention groups at the end of the treatment period. ANCOVA will be the primary approach used for the analysis. We will employ White's robust (information sandwich) estimate of the covariance matrix of the model coefficients as the basis for inferences. This approach preserves power and protects the type 1 error probability when the homoscedastic normal errors assumptions are violated. All analyses will be adjusted for the baseline value of each endpoint. Both primary outcomes will be analyzed separately with a total type I error probability of 0.05 for each, i.e. without an adjustment for 2 separate outcomes.

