# 6.2 Main Study Procedures

The timing of major study procedures is illustrated in the Figure 3, Section 3 above. Data to determine main study outcomes using hyperglycemic clamp procedures will be obtained at baseline and study end, which will be defined as either the end of 24 months after initiation of metformin or placement of gastric band, or at the time of treatment failure (A1C >8.0% on two successive visits). Data for secondary analyses will be determined at other study visits. Blood and urine samples will be collected for planned measures and extra blood and urine samples will be stored for future analyses. Further details on these measures are provided below, and are summarized in Table 6.2.

	Baseline	2-mo	4-mo	6-mo	8-mo	10-mo	12-mo	15-mo	18-mo	21-mo	24 mo
Exam	X	X	Х	Х	Х	Х	Х	Х	X	Х	Х
OGTT	X						Х				Х
Hyperglycic Clamp	X						Х				Х
DEXA	X						Х				Х
MRI	X						Х				Х
A1C	X		Х	Х		Х	X		X		Х
Fasting/Biomarkers	X			Х			Х		X		Х
Band Questionnaires	X			Х			Х		X		Х
Sleep Questionnaires	X										
Clinical Labs-1	X			Х			Х		X		Х
Clinical Labs-2				Х			Х		X		Х

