## 6.2.3 Hyperglycemic Clamp

Hyperglycemic clamps (at approximately 200 mg/dl) will be performed after a 10-12 hour overnight fast at baseline and at 12 and 24 months after initiation of metformin or placement of gastric bands. The clamp procedure will incorporate 3 main sets of blood sampling for the planned outcome measurements: first phase (0-10 minutes); second phase (100-120 minutes); and maximal stimulated responses (from 10 minutes before until 10 minutes after arginine injection once plasma glucose has been raised to~450 mg/dl). A priming glucose bolus will be used to stimulate first phase responses, a continuous dextrose infusion will be used to create steady state hyperglycemia at ~200 mg/dl for second phase and then raise glucose to ~450 mg/dl for maximum response to arginine. Arterialized venous blood samples will be obtained at 5-min intervals throughout for measurement of plasma glucose concentration to guide the glucose infusion.

For the OGTT and clamp measures, participants will be asked to refrain from vigorous exercise and tobacco use for 24 hours before the initiation of testing. Study medications will be withheld the morning of testing.

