#### 7.4.6 Hyperglycemia

Participants are instructed regarding the signs and symptoms of hyperglycemia and are to call the clinic with any concerns. HbA1C will be measured at six-month intervals. If a value exceeds 7%, therapy is invigorated by frequent telephone contact and/or visits to encourage optimal medication adherence and lifestyle choices. If a scheduled HbA1C exceeds 8.0% the test will be repeated one month later. If the value remains >8.0%, end-of study testing is performed and the participant completes participation in the study and is referred for standard care of diabetes.

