# 9.2 Secondary Outcomes and Analyses

Comparisons of the primary study outcomes will be made for those with vs. without diabetes at study entry, BMI <35 kg/m2 vs. ≥35 kg/m2 at study entry, by race/ethnicity and sex, by baseline HbA1c and β-cell function, and by categorical groups of various biomarkers.

Analysis of covariance will be used to compare the metformin and gastric band groups for additional continuous variables of interest at both the 12-month and 24-month time points relative to the start of the interventions. As for the primary outcomes, all analyses will be adjusted for the baseline value of each endpoint.

An important secondary analysis of this study is to determine whether ß- and  $\alpha$ -cell function from OGTT and fasting samples are sufficiently well correlated with more robust assessments of ß- and  $\alpha$ -cell function obtained from the hyperglycemic clamp to validate their use in large clinical trials. For these analyses, Pearson and non-parametric Spearman correlations of simple versus sophisticated measures of ß- and  $\alpha$ -cell function will be computed.

To examine biomarker associations with glucose metabolism, Pearson and non-parametric Spearman correlations of each biomarker with ß- and  $\alpha$ - cell function, insulin sensitivity and glucose tolerance measures will be determined. In addition, multiple linear regression models

will be developed to predict measures of glucose metabolism with the most informative biomarker sets.

Other planned secondary analyses will examine relationships between exposure variables such as body weight and fat, insulin resistance; circulating adipokines and fat metabolites, and glucose levels and primary and secondary β-cell outcomes within and across treatment groups.

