# 9.5 Handling of Missing Data

It is anticipated that a small number of participants may reach HbA1C >8.0% on two visits and, thus, have primary outcomes completed prior to 24-months. If follow-up time between baseline and end-of-trial differ between the two intervention groups, we will use rate of change (defined as (baseline-end-of-trial)/follow-up time) as the outcome in the analysis to take into account of differential follow-up time.

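### The plan has no rule for participants without an end-of-study clamp, and its switch to rate of change has no defined trigger

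*Combined protocol and SAP*

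**What the plan says.** **Primary analysis.** Section 9.1: "ANCOVA will be the primary approach used for the analysis", adjusted for baseline, with a robust variance. Section 6.2: "Data to determine main study outcomes using hyperglycemic clamp procedures will be obtained at baseline and study end". The same section adds: "Data for secondary analyses will be determined at other study visits".

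**12-month clamp.** Section 6.2.3 schedules clamps "at baseline and at 12 and 24 months after initiation of metformin or placement of gastric bands". Section 9.2 uses ANCOVA "for additional continuous variables of interest at both the 12-month and 24-month time points", which leaves the 12-month clamp outside the primary model. Section 5.4, however, says that main outcomes are to be assessed at both 12 and 24 months. It lists a change to rates of change among options to explore if dropout exceeds 10% per year.

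**Missing data.** Section 9 promises intention-to-treat analysis "using all available data from all subjects". Section 3.4.1 sends the reader to a Section 9.6 for drop-outs. The table of contents gives missing data that number, but in the body it is 9.5. Section 9.5 deals only with participants who leave early because of HbA1c, and Section 7.4.6 gives these a final clamp: "If the value remains >8.0%, end-of study testing is performed and the participant completes participation in the study".

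**Switch of outcome.** Section 9.5: "If follow-up time between baseline and end-of-trial differ between the two intervention groups, we will use rate of change". It gives no size of difference, no test and no decision date. Section 3.1 already calls the primary outcome a rate of change, Section 3.2 calls it change from baseline to end of study, and Section 9.1 compares groups at the end of treatment.

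**The concern.** Two decisions that shape the primary result are left open in a trial without masking (Section 4.6).

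The first is what happens to a randomised participant with no end-of-study clamp. An ANCOVA of the end value drops such a person unless told otherwise. That is harmless if loss depends only on arm and baseline. It biases the contrast if people leave because of how they responded by 12 months, and do so differently in the two arms. The 12-month clamp carries information about exactly that, and it is already scheduled.

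The second is which form of the outcome is tested. Section 9.5 replaces the outcome on the basis of observed follow-up times. Metformin starts the day after the second baseline visit, whereas banding is aimed for within two weeks (Section 4.5). Section 6.2 counts study end from the start of metformin or placement of the band. Time from baseline to end would then be longer in the band arm by design, and the switch could trigger without a single early exit.

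**Working it through.** **1. The plan's own figures (Section 9.3).** Inputs: 44 per arm, 10% loss per year, two-sided 0.05, baseline correlation 0.5.
- Completers: 44 × 0.9² = 35.6, or 44 × 0.8 = 35.2; stated about 35.
- t-test, 35 per arm, effect 0.68: power 80.1% (stated 80%).
- ANCOVA, residual SD √(1 − 0.5²) = 0.866: power 89.9% at 0.68 (stated 89%) and 80.2% at 0.59 (stated 80%).

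The figures are sound. They are sized on participants with a final clamp.

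**2. Who is affected, per arm.**
- With a 12-month clamp: 44 × 0.9 = 39.6.
- With an end clamp: 35.6, so 44 − 35.6 = 8.4 without one.
- 12-month but no end clamp: 39.6 − 35.6 = 4.0.
- No follow-up clamp: 44 × 0.1 = 4.4.

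**3. Precision from the 12-month clamp, random loss.** With ρ the 12/24-month partial correlation given baseline, the per-arm variance is proportional to (1 − ρ²)/35.64 + ρ²/39.6. The 12/24-month correlation r is not in the documents; assume 0.5 to 0.8, with 0.5 between baseline and each visit. Then ρ = (r − 0.25)/0.75. For r = 0.7, ρ = 0.6 and 0.64/35.64 + 0.36/39.6 = 0.02705, an effective n of 37.0. Over the range, effective n is 36.0 to 37.7 and power at 0.59 rises from 80.9% to 81.4–83.1%. The gain is small.

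**4. Bias, by simulation (10,000 trials per setting).** Assumed:
- correlations 0.6 (baseline/12 months), 0.5 (baseline/end) and 0.7 (12 months/end);
- 10% lost at random before 12 months, then 10% lost with odds ratio 4 per SD lower 12-month value, in one arm only;
- HbA1c exits with an end clamp: none / 2% before and 5% after 12 months / 2% and 10%.

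| True effect 0.59 | ANCOVA of available end clamps | Power |
|---|---|---|
| Selective loss, metformin only | 0.540 / 0.568 / 0.581 | 73 / 78 / 79% |
| Selective loss, band only | 0.638 / 0.633 / 0.625 | 86 / 86 / 85% |
| Likelihood model with 12-month clamp | 0.587–0.595 | 81–82% |
| Imputation by arm with 12-month clamp | 0.586–0.593 | 79–81% |

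- Repeat runs of the no-exit setting gave 0.546 (metformin only) and 0.635–0.637 (band only).
- Random or equally selective loss: no bias. Type I error: 4.8–5.5% (ANCOVA) and 4.7–5.2% (likelihood model).
- At the projected effect of 0.80, ANCOVA power is 94–98%.
- At other correlations, one-arm bias with no exits ranges from about 0.03 (0.5/0.5/0.5) to 0.06 (0.6/0.5/0.8). Selection in opposite directions in the two arms gives 0.07 to 0.10.
- If loss depends on the unseen end value (odds ratio 4, one arm), ANCOVA gives 0.500 or 0.682 and the likelihood model 0.529 or 0.653. Only about a third of the bias is removed.

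**5. Tipping point.** SE = √(0.75 × 2/35.64) = 0.205, so significance needs 1.995 × 0.205 = 0.409. A shift in the 19% lost from one arm must reach (0.59 − 0.409)/0.19 = 0.95 SD, or (0.80 − 0.409)/0.19 = 2.1 SD, to overturn the result.

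**6. The switch.**
- *Trigger.* Assume a 14-day lag and a visit-timing SD of 7 to 30 days. At 30 days the SE of the difference is 30 × √(2/35.64) = 7.1 days and 14/7.1 = 1.97, so a 5% test finds a difference in about 49% of trials. At 7 days it does so in essentially 100%.
- *Effect.* A change measured at 7 months (six-month test plus one-month repeat) is scaled to 24 months by 24/7 = 3.4. With 2% + 5–10% exits, power at 0.59 was 77% for rate and 81% for end value, with different verdicts in 6–7% of trials. With 2 to 6 exits, all on metformin, it was 80–82% for rate and 78–79% for end value. Neither form is uniformly better.
- *Type I error.* Applied mechanically, 4.7–5.1%. Choosing whichever form is significant, with 2 to 6 exits, 5.6–6.8%.

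**The case against.** A reader might infer that the plan commits to a completer analysis and discards the 12-month clamp. The documents do not go that far. Section 9 promises all available data, and Section 5.4 expects main outcomes at 12 and 24 months. The dropping of participants follows from Sections 9.1 and 6.2 read together. What stands is that the promise has no mechanism, and that Sections 5.4 and 6.2 need reconciling.

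A reader might also infer that the team could change the outcome freely. The option in Section 5.4 has an entry threshold (loss above 10% per year), and such a change would need approval by the Data and Safety Monitoring Board (Sections 7.1 and 11.9). Those safeguards do not reach the switch in Section 9.5, which is already in the plan. Its trigger is follow-up time, however, not clamp results. The authors probably did not mean any trivial difference in days, but the text does not say what they did mean. The built-in lag also depends on counting from treatment start. Section 6.3 counts visits from randomisation, and if that calendar governed the final clamp the lag would disappear.

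Finally, the harm is small and rests on loss that is selective in one arm, which nothing in the documents predicts. That is correct, and it sets the weight of the point.

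**Conclusion.** The point holds as an omission worth closing, not as a flaw that threatens the trial. About 8 per arm are projected to have no end clamp, no section says how they enter, and about 4 of them would have a 12-month clamp that the stated primary model leaves out. The switch in Section 9.5 has no operable trigger and, on the timing in Sections 4.5 and 6.2, could fire because of the design itself.

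The expected size is modest. There is no bias under random or equally selective loss. Bias is about 0.05 SD or less in the main setting if loss after 12 months depends on the 12-month value in one arm only, at an assumed odds ratio of 4 per SD. Its direction depends on the arm: selective loss on metformin understates the band effect (power 73 to 79% against about 81%), and selective loss on banding overstates it. Harsher assumptions give more. Type I error stays near 5% if the switch is mechanical, and about 5.6 to 6.8% if the favourable form is chosen. The stronger conclusions, that the primary result will be biased or its error rate materially inflated, are not supported. The correlations other than 0.5, the dropout mechanisms and the visit scatter are all assumptions.

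**What to change.** - **Primary model (9.1, 9.5).** For each co-primary endpoint, prespecify a likelihood-based repeated-measures model of the 12-month and study-end clamps, adjusted for baseline, with the study-end contrast as the primary test. Multiple imputation by arm using the 12-month clamp, followed by the planned ANCOVA with White's variance, is an acceptable alternative. Keep the planned ANCOVA as a sensitivity analysis.
- **One form of the outcome.** Align Sections 3.1, 3.2, 5.4, 9.1 and 9.5 on change to study end. Make rate of change a prespecified sensitivity analysis, with no switch decided by observed follow-up times. State whether the 24 months run from randomisation or from treatment start.
- **HbA1c exits.** State that the exit clamp enters as the study-end value, as Section 6.2 defines study end, and acknowledge that this assumes no further change after exit. With an assumed mean decline of 0.5 to 1 SD over 24 months and a true effect of 0.59, end-value estimates were 0.56 to 0.58 and rate-based ones 0.62 to 0.64, so the assumption costs little.
- **Missing not at random.** Add a tipping-point analysis whose shifts extend until the conclusion changes. Step 5 suggests going past 2 SD if the effect is near 0.80.
- **Cross-reference.** Correct the section number in 3.4.1.

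**Cost.** Wording and some programming; no new data. The model relies on loss being at random given arm, baseline and 12-month value. The precision gain is a few percent at most, and imputation showed none. It does not help the 4.4 per arm lost before 12 months. Because the endpoints are shared across the RISE consortium (Sections 3.2 and 11), the model should be agreed there.
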